1.0 Introduction

Parallel opposed portal external beam radiation is the standard nonsurgical treatment for T1-2N0 glottic cancer.¹ This technique involves treatment of the entire larynx for tumors that are small and limited. Although technological advances now allow radiation oncologists selectively to target and avoid adjacent sub-portions of any organ, these tools have not been applied T1-2N0 glottic cancer due to the perceived low toxicity of standard therapy. However, radiotherapy for early glottic cancer is not without functional side effects² and it is not known whether post-treatment function after whole larynx radiation is superior to a more targeted surgical approach³

This is a phase II study to treat unilateral glottic cancer (Stage T1a and T2aN0) with intensity modulated radiation therapy (IMRT). In view of the anticipated small volume of disease at presentation and need to limit the potential for a “marginal miss”, treatment will include the entire involved vocal fold, anterior commissure, and the anterior 1/3 of the contralateral vocal fold thus sparing the contralateral arytenoid cartilage and musculature (“contralateral arytenoid sparing IMRT”). In addition, we propose to perform sophisticated objective and patient reported measures regarding speech outcomes for two years after the completion of therapy at specified intervals, to better gain an understanding of the effects of therapy. Our findings will have the potential to dramatically advance the field of early larynx cancer therapy by demonstrating the efficacy of limiting the volume of uninvolved larynx that receives radiation and comprehensively assessing the functional outcomes of said therapy.

1.1 Study Rationale

T1-2N0 glottic squamous cell carcinoma (SCC) is traditionally treated with simple, parallel opposed radiation fields⁴ with a gratifying control rate^{1,5-7}. Although the technological sophistication of the administration of external beam radiation has increased dramatically in the past 50 years, treatment of early stage larynx cancer has changed little since 1964⁵. The reason for this is twofold: the efficacy of radiation therapy prescribed in this manner and the perceived low toxicity of treatment.

The favorable toxicity profile of parallel opposed radiation for early glottic tumors is largely a result of the low incidence of nodal metastases⁸, permitting omission of elective nodal irradiation from treatment plans. Thus, most radiosensitive normal tissues⁹ are clear of the radiation field. Large single-institution retrospective experiences of both primary radiation^{5,10} and transoral surgery⁸ report long term serious complications on the order of 1%. Randomized trials of primary radiation^{6,7,11} report higher rates of long term toxicity, approaching 10%, perhaps due to more careful prospective reporting. The combination of low long term toxicity and excellent efficacy is appealing, however early larynx tumors are typically quite small⁸ and parallel opposed radiotherapy results in treatment of the entire larynx, complicating salvage operations when necessary. Typical head and neck radiation assessments of toxicity¹² may not be applicable.

The excellent treatment outcomes of early larynx cancer and its incidence ¹³ (which may be rising) suggest that survivorship concerns merit greater consideration than previously afforded in the reported experiences. One facet of head and neck cancer survivorship that can uniquely be addressed in early larynx cancer is radiation dose to the carotid arteries, because elective lymphatic radiation is not required. External beam radiotherapy is an independent risk factor for accelerating carotid atherogenesis ¹⁴; head and neck cancer patients treated with radiation have been demonstrated in some data sets to have an increased risk of ischemic stroke ^{15,16}. In parallel opposed radiation, the carotid arteries generally receive a dose of radiation similar to that of the tumor (Figure 2). By contrast, they can be significantly avoided without compromising target coverage through IMRT, and pilot studies have demonstrated encouraging results with this technique ¹⁷.

and vibration using a strobe light source. These recordings will then be evaluated for amplitude, symmetry, and periodicity of the vocal fold mucosal wave; presence or absence of glottic closure; and degree of mobility by measuring the angle of abduction of each vocal fold from the midline. The most widely used subjective patient perception tool is the VHI, which is a validated, self-administered 30 item questionnaire covering three domains: functional, physical, and emotional (APPENDIX) ²⁸. This questionnaire will be administered at each visit and takes less than 10 minutes to complete.

Deglutition changes following treatment of early glottic carcinomas with radiation are not well-studied. Peretti et al. reviewed swallow outcomes following transoral laser surgery for T2-T3 cancers, and found that up to 4% of patients develop aspiration with high patient-perceived difficulty with swallowing²³. Another study reviewed quality of life concerns in patients who had undergone endoscopic laser resection of T1-T2 cancers, and found that two issues of highest concern to recovering patients were salivary production/control and swallowing²⁹. Similar data are unavailable for patients undergoing radiation therapy.

The proposed study will therefore include objective and subjective measures of swallow function. Objective evaluation will be employed using the Penetration-Aspiration Scale as well as the Functional Outcome of Swallowing Scale ^{30,31}. Subjective evaluation will be performed using the validated EAT-10, which is a 10 item self-administered questionnaire that takes 1-2 minutes to complete ³²

2.0 Objectives

To define a new treatment technique for T1a larynx cancer that maintains excellent local control with less extensive radiation fields

Hypothesis: Contralateral arytenoid sparing IMRT for T1a larynx cancer maintains the excellent local control associated with whole larynx radiation and results in functional outcomes at 24 months after therapy that are suggestive of improved function when compared to historical controls

2.1 Primary Objectives and Endpoints

Voice quality outcomes at 24 months after contralateral arytenoid sparing IMRT for T1a/T2a larynx cancer

Two year local control with contralateral arytenoid sparing IMRT for T1a/T2a larynx cancer

2.2 Endpoints

2.1.1 Primary endpoint

Demonstrate a 50% improvement in the VHI (voice handicap index) score at 24 months after the completion of therapy

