11.0 Statistical Analysis

This is a single arm phase II trial. Prior head and neck investigations of IMRT to minimize 3D conformal toxicity have anticipated (and demonstrated) a 30% decrease in symptoms when IMRT is utilized³⁸. Non-randomized analyses have suggested that the benefit of IMRT approaches a 50% decrease in symptoms³⁹. Thus, to be conservative, the null hypothesis of this analysis is that two year VHI scores will be 33% lower than baseline. This represents a decline from an average VHI global score of 44 to about 29, a decline of 15 points. Our alternative of interest is a 50% decline in VHI global score, a decline of 22 points. L. Di Nicola et al (ref) tabulated such scores and we have taken their estimate of the standard deviation at baseline of VHI global score, std = 8.5. We used this same value for the 2 year score, which is not given by Di Nicola, but is close to the 3 year score when VHI scores have further declined. This, in turn, gives the std of baseline less 2 year scores of 8.5 times 1.414. VHI average scores are estimated to be normally distributed.

We will obtain baseline and 2 year VHI scores for an initial cohort of 15 patients. We will terminate the study after the first 15 patients have been evaluated at 2 years if their average decline is less than 15. Otherwise we will recruit an additional 15 patients. If the overall average of all 30 patients is at least 19.2 we will reject the null hypothesis. The design has 50% chance of early stopping under the null and a 2.58% chance of early stopping in error. The overall type I error is 5% and the study power is 85%.

We will test the null hypothesis that at most 85% of patients will achieve local control versus the alternative that at most 95% of them will. If less than 13 of the initial cohort

of 15 experience local control, we will interrupt the study for futility. If at least 28 of 30 acquire local control we will reject the null and declare the local control rate to be 95%. The chance of early stopping for lack of local control is 40% when the true local control rate is 85%. The chance of early stopping in error is 3.6%. The overall power is 81% and overall type I error is 15.1%.

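### The primary endpoint promises to show a 50% VHI improvement, but the decision rule tests against a 33% decline and can succeed at a mean decline of 19.2 points, 43.6% of the assumed baseline

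*Combined protocol and SAP*

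**What the plan says.** Section 2.1.1 states the primary endpoint as "Demonstrate a 50% improvement in the VHI (voice handicap index) score at 24 months after the completion of therapy". It does not say what the 50% is relative to, nor whether it concerns a group mean or individual patients.

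Section 11.0 sets out the test:

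- Null: "the null hypothesis of this analysis is that two year VHI scores will be 33% lower than baseline". In points: "This represents a decline from an average VHI global score of 44 to about 29, a decline of 15 points".
- Alternative: "Our alternative of interest is a 50% decline in VHI global score, a decline of 22 points".
- Interim rule: "We will terminate the study after the first 15 patients have been evaluated at 2 years if their average decline is less than 15".
- Success rule: "If the overall average of all 30 patients is at least 19.2 we will reject the null hypothesis".

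No rule in the document tests against a 50% decline or requires an observed decline of 50%. The hypothesis in sections 2.0 and 2.4 is softer than either statement: it speaks of functional outcomes that suggest improvement over historical controls.

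**The concern.** An endpoint that is to be demonstrated should be what a positive test establishes. Here the endpoint names the effect used to compute power, while the test rejects a smaller effect. Rejecting a 33% decline is evidence for a decline larger than 33%; it does not establish the alternative.

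On the same data the two sections can point in different directions. If the mean decline is at least 19.2 but below 22 points, section 11.0 rejects the null, while the 50% in section 2.1.1 is not reached even as a point estimate (at a mean baseline of 44). What is at stake is the claim a positive trial may make about its primary endpoint: a reader who takes 2.1.1 at its word could read success as proof of a halved VHI.

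**Working it through.** **Inputs, all from section 11.0.** Mean baseline 44; null decline 15; alternative decline 22; interim cut-off 15 at n = 15; final cut-off 19.2 at n = 30; normal distribution; SD of change from "gives the std of baseline less 2 year scores of 8.5 times 1.414", that is 8.5 × 1.414 = 12.02.

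**1. The plan's own operating characteristics.** The standard errors are 12.02/√15 = 3.10 and 12.02/√30 = 2.19. The probability of success is P(mean of 15 ≥ 15 and mean of 30 ≥ 19.2), bivariate normal with correlation √(15/30) = 0.707.

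| | Stated | SD 12.02 | SD 14 |
|---|---|---|---|
| Early stop under null | 50% | 50% | 50% |
| Early stop under alternative | 2.58% | 1.2% | 2.6% |
| Type I error | 5% | 2.7% | 4.9% |
| Power | 85% | 89.6% | 85.7% |

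The printed SD gives only the first figure; an SD near 14 gives roughly all four. That discrepancy is a separate matter. Both SDs are carried below so that the conclusion does not hang on it.

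**2. The cut-off as a percentage of baseline.** 15/44 = 34.1%; 19.2/44 = 43.6%; 22/44 = 50%. The rule is in points, so the percentage moves with the enrolled mean baseline: 19.2/40 = 48%, 19.2/50 = 38.4%, and 19.2/38.4 = 50%. The cut-off equals an observed 50% decline only at a mean baseline of 38.4.

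**3. What an observed 19.2 supports.** Naive one-sided 95% lower bound, ignoring the interim look: 19.2 − 1.645 × SE.

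- SD 12.02: 19.2 − 1.645 × 2.19 = 15.6 points (35% of 44).
- SD 14: SE = 14/√30 = 2.56; 19.2 − 1.645 × 2.56 = 15.0 points (34% of 44).

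Either way the bound lies at about one third of baseline, far from 22 points.

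**4. What demonstrating 50% would take.** For the same bound to reach 22, the observed mean must be 22 + 1.645 × SE: 22 + 3.6 = 25.6 points with SD 12.02 (58% of 44), or 22 + 4.2 = 26.2 points with SD 14.

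**5. How often success would come with an observed mean below 22.** This is P(success) minus P(mean of 15 ≥ 15 and mean of 30 ≥ 22). If the true decline is exactly 22:

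- SD 12.02: 0.896 − 0.500 = 0.396, about 40% of all trials.
- SD 14: 0.857 − 0.500 = 0.357, about 36%.

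**The case against.** The strongest reply is that nothing is wrong with the design. A test of 33% against 50% is ordinary, section 11.0 states every element openly, and with power well above 50% the cut-off has to lie below the alternative. This stands. A reader might infer that 19.2 is set too low or that the hypotheses are wrong; the documents do not support that.

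Second, section 11.0 alone governs stopping and success, and no section makes an observed 50% decline a further criterion. This also stands: between 19.2 and 22 points there is one formal verdict, rejection of the null. The mismatch is between that verdict and what 2.1.1 says will have been shown.

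Third, a reader might infer that the sponsor will report a positive trial as a demonstrated 50% improvement. The documents do not say so. For VHI, section 11.0 says only that the null will be rejected, and the hypothesis in 2.0 and 2.4 is modest. The risk is not fanciful, because for local control the same section does say that meeting the cut-off will lead to the rate being declared as 95%. For VHI it remains a possible misreading, not a stated intention.

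Fourth, reading the 50% as relative to baseline is inferred, and 43.6% needs a mean baseline of 44. Both are fair qualifications. Section 11.0 expresses its own 50% as a decline from baseline, and 44 is the protocol's own figure. With a mean baseline of 38.4 or lower, every success would also show an observed decline of at least 50%; even then, an observed 50% would not demonstrate a true one.

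**Conclusion.** The point holds as a mismatch between the endpoint wording and the decision rule. Section 2.1.1 presents the powering alternative as the thing to be demonstrated, whereas success under section 11.0 supports only a decline greater than about one third. At the cut-off the observed decline is 43.6% of the assumed baseline, with a lower bound of about 15.6 points (printed SD) or 15.0 points (SD near 14). With a true decline of exactly 22 points, about 40% of trials would succeed with an observed mean below 22 on the printed SD.

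These figures assume that the 50% is relative to baseline, that the enrolled mean baseline is 44, that changes are normal, and that the bound may ignore the interim look. The choice of SD changes the numbers slightly and leaves the conclusion as it is. The finding does not extend to the hypotheses, the sample size or the cut-off.

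**What to change.** Keep the hypotheses, sample size and cut-off, and change the wording in two places.

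- Section 2.1.1: 'Mean decline in VHI from baseline to 24 months after completion of therapy, tested against a 33% decline; the study is powered for a 50% decline.'
- Section 11.0: add that reaching 19.2 points supports only a decline greater than the null, that the mean decline will be reported with its confidence interval, and that no 50% improvement will be claimed unless the interval supports it. Name the interval. A one-sided 95% bound matches the one-sided form of the rule; with the printed SD, the two-sided 95% interval at 19.2 is 14.9 to 23.5 points and would just include the null.

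This adds no patients, visits or analyses. The cost is that the claim available from a positive trial becomes less favourable.

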2.2.2 Secondary Endpoints

Demonstrate a similar 2-yr local control of (>85%) with IMRT therapy for T1a and T2aN0 larynx cancer

Evaluate clinician-reported voice quality at defined intervals up to 24 months after the completion of radiation using the Grade, Roughness, Breathiness, Asthenia, and Strain (GRBAS) scale

Use the Eating Assessment Tool (EAT-10) to evaluate patient-reported satisfaction with swallowing at up to 24 months after the completion of radiation

Evaluate clinician-reported measures of swallowing 24 months after the completion of radiation as measured by fiberoptic endoscopic evaluation of swallowing (FEES) using the penetration, aspiration scale (PAS) scores for 3 commonly evaluated textures (cookie, puree, thin).

2.3 Purpose/Specific Aim of this Research Study: To define a new treatment technique for T1a larynx cancer that maintains excellent local control with less extensive radiation fields

2.4 Hypothesis: Contralateral arytenoid sparing IMRT for T1a larynx cancer maintains the excellent local control associated with whole larynx radiation and results in functional outcomes at 24 months after therapy that are suggestive of improved function when compared to historical controls

3.0 Study Plan

3.1 Description of Study Design, Population and Duration of Study Therapy

This is a single arm phase II study. All subjects will be treated with the standard fractionation for T1a glottic cancer at FCCC: 63 Gy in 28 fractions⁶ for T1a and 65.25 Gy in 29 fractions³³ for T2a.

Subjects will be patients referred to FCCC or Temple for treatment of T1 glottic cancer. Patients will be approached for trial accrual during the pretreatment process. Patients will be provided with the informed consent document to educate themselves regarding the rationale of the study. Patients with T1a larynx cancer that agree to the functional assessment of the study will be identified as potential candidates. The duration of protocol assessment is 24 months.

Subjects will be seen in follow-up at least every 3 months for the first year and every 4 months for the second year after therapy for tumor surveillance, consistent with the standard of care.

Subjects will also be seen by speech therapy on a separate schedule, consistent with current institutional practice of voice rehabilitation after this therapy. At the 1,3,6,12, and 24 months follow-up patient reported questionnaires and functional assessments will be captured and recorded

Number of subjects per year projected at FCCC/Temple	Total number of subjects at FCCC/Temple	Number of subjects nationally or internationally (if applicable)	Number of subjects at collaborating institutions (if applicable)
Up to: 4	Up to: 30	0	0

4.0 Patient Selection Inclusion & Exclusion

4.1 Inclusion Criteria

4.1.1 Patients with histologically proven invasive squamous cell carcinoma arising from the true vocal cord.

4.1.2 T1a and T2a squamous cell carcinoma of the glottic larynx (tumor limited to one vocal cord with normal cord mobility).

4.1.3 Squamous cell carcinoma in-situ of a single vocal cord (Tis) is eligible.

4.1.4 Minimum age of entry is 18 years.

4.1.5 Patients must be able to read and write English to comply with the questionnaire portions of the protocol.

4.1.6 ECOG performance status of 0 or 1.

4.2 Exclusion Criteria

4.2.1 Patients with verrucous or adenocarcinoma

4.2.2 Patients with T1 tumors on both cords (T1b)

4.2.3 Patients with T2b-T4 true larynx tumors

4.2.4 Patients with primary supraglottic tumors that involve the true larynx

4.2.5 Patients with a prior or concurrent malignancy (other than non-melanoma skin cancer or carcinoma in-situ of the cervix) are ineligible unless the previous cancer was treated 5 years or more prior to the current tumor and the patient has remained continually disease free

4.2.6 Prior radiation to the head and neck

4.2.7 Pregnant or breastfeeding. A negative blood-pregnancy test is required for women of childbearing potential (WOCBP) within 14 days prior to her CT stimulation for treatment planning. Refer to section 4.4 for further detail.

4.3 Inclusion of Women and Minorities

Men and women, regardless of race, ethnic group or sexual orientation are eligible for this study.

4.4 Pregnancy

The effects of radiation therapy on the developing human fetus at the recommended therapeutic dose are known to be teratogenic. For this reason women of child-bearing potential (WOCBP) and men must agree to use adequate contraception (hormonal or barrier method of birth control; abstinence) prior to study entry, for the duration of treatment. Should a woman become pregnant or suspect she is pregnant while participating in this study, she must inform her treating physician immediately.

Prior to study enrollment, WOCBP must be advised of the importance of avoiding pregnancy during trial participation and the potential risk factors for an unintentional pregnancy. In addition, men enrolled on this study should understand the risks to any sexual partner of childbearing potential.

All WOCBP must have a negative pregnancy test within 14 days prior to CT stimulation for treatment planning. If the pregnancy test is positive, the patient must not receive the CT nor protocol treatment and must not be enrolled in the study.

WOCBP is defined as follows: Any female who has experienced menarche and who has not undergone successful surgical sterilization (hysterectomy, bilateral tubal ligation, or a bilateral oophorectomy) or is not postmenopausal (defined as amenorrhea \geq 12 consecutive months, or women on hormone

replacement therapy (HRT) with documented plasma follicle-stimulating hormone (FSH) level > 35 mIU/ml). Even women who are using oral, implanted, or injectable contraceptive hormones or mechanical products (diaphragm, condoms, spermicides) to prevent pregnancy or practicing abstinence or where partner is sterile (e.g. vasectomy), should be considered to be WOCBP.

4.5 Patient Registration

Participants may be registered from 8:00 am to 5:00 pm EST excluding holidays by emailing the Investigator-Sponsored Research Unit (ISRU) at:

[contact]. Eligible participants will be entered on study centrally once the following items have been received by email:

- Completed registration form
- Consent and HIPAA signature pages
- Eligibility checklist

Following registration, participants must begin protocol treatment within 14 calendar days of registration. Issues that would cause treatment delays must be discussed with the Sponsor-Investigator. If a registered participant does not receive protocol therapy following registration, the participant will be recorded as withdrawn from study. The Study Monitor must be notified as soon as possible if a participant does not begin protocol treatment as scheduled. For additional registration questions, please email **[contact]** or call **[contact]**.

The FCCC ISRU will notify the site by email once registration is confirmed and the sequence number has been assigned. Participants must be registered and have received a sequence number prior to the initiation of treatment.

Exceptions to the current registration policies will not be permitted.

5.0 Treatment Plan

This is a single arm phase II study. All subjects will be treated with the standard fractionation for T1a glottic cancer at FCCC/Temple: 63 Gy in 28 fractions⁶ for T1a and 65.25 Gy in 29 fractions³³ for T2a as detailed below.

5.1 Targets

5.1.1 The immobilization device must include neck and shoulder immobilization. An aquaplast face mask is required. The shoulders can either be immobilized by a shoulder depression device or an extended aquaplast configuration

5.1.2 Treatment planning CT scan in the immobilized position will be required to define the tumor, clinical and planning target volume.

5.1.3 CT thickness must be ≤ 3 mm for the CT simulation. The CT must include the entire larynx

5.1.4 The GTV, CTV, and PTV and normal tissues must be outlined on the CT slices in which they exist

